9.3.3.1. AE of special interest identified by PTs

The number and percentage of subjects experiencing these TEAEs of special interest will be summarized for each treatment group by type of event. The incidence rate of AE of special interest per 100 patient years will also be summarized. Each category of events will be displayed in a separate listing.

9.3.3.2. Hypoglycemic Events

Hypoglycemic event categories include:

1007728

Category	Description
Severe	Assistance required and blood glucose ≤70 mg/dL or no value available but responded to glucose treatment
Documented Symptomatic	Blood glucose ≤70 mg/dL and typical symptoms of hypoglycemia
Asymptomatic	Blood glucose ≤70 mg/dL and no typical symptoms of hypoglycemia
Probable Symptomatic	Typical symptoms of hypoglycemia and no value available but responded to glucose treatment
Relative	Typical symptoms of hypoglycemia and blood glucose >70 mg/dL

While each event meeting the criteria above will be entered into the hypoglycemia log, only critical (severe) hypoglycemia, documented symptomatic hypoglycemia, asymptomatic hypoglycemia, and probable hypoglycemia will be entered as AEs.

The number and percentage will be summarized by treatment for:

- Each category of hypoglycemic events;
- Any severe or documented hypoglycemic events.

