3.2.3.3 Main Treatment

During the 24-week treatment period, subjects will be advised to continue daily fasting SMBG measurements. Subjects should contact the clinic if any fasting SMBG is \geq 270 mg/dL (15 mmol/L) from week 1 to week 6, \geq 240 mg/dL (13.3 mmol/L) after week 6 to week 12, or \geq 200 mg/dL (11.1 mmol/L) after week 12 to week 24. Blood glucose values collected via SMBG will be evaluated at study visits by the investigator. In addition, hyperglycemia will be monitored by fasting plasma glucose (FPG) measurement at each study visit.

If hyperglycemia is identified through SMBG or FPG measurements, the investigator will first determine whether the subject had fasted for approximately 10 hour prior to the blood draw to ensure that the FPG value is truly a fasting sample. If proper fasting had not occurred, the subject should be asked to return for a repeat blood test within a week.

During the treatment period, hyperglycemia should be managed first with diet and exercise counseling and should be managed with changes in the medical therapy only if the investigator feels it is necessary for the well-being of the subject (see below, *Prescription of Rescue Medication*). After the treatment period, changes to the medical therapy for hyperglycemia should occur at the discretion of the investigator based on SMBG, FPG, and HbA1c information using local standards of care for subjects with T2DM.

If a concomitant medication for hyperglycemia is to be prescribed, a blood sample must be drawn prior to the administration of the rescue medication so that a final HbA1c value can be determined.

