3.2.3.4 Prescription of Rescue Medication

Rescue medication for hyperglycemia should be prescribed by the investigator at any time it is deemed necessary for the well-being of the subject. During the 24 week treatment period, a review of diet and exercise counseling is suggested prior to prescription of rescue medication in the absence of specific medical indications for rescue medication. Rescue medication is suggested during the treatment period if, after a review of diet and exercise counseling:

- more than 3 consecutive, daily, fasting SMBG measures are ≥ 270 mg/dL (15 mmol/L) from week 1 to week 6, ≥ 240 mg/dL (13.3 mmol/L) from week 6 to week 12, or ≥ 200 mg/dL (11.1 mmol/L) from week 12 to week 24
- 2. persistent clinical signs or symptoms of hyperglycemia are present (*e.g.* weight loss, blurred vision, increased thirst, or increased urination, or fatigue)

The investigator may provide rescue treatment with any approved medication for diabetes that is not otherwise contraindicated, with the exception of an SGLT2 inhibitor.

Subjects who receive rescue medication due to poor glycemic control will continue to receive investigational product and standard of care per investigator decision, according to current treatment guidelines, during the treatment period. Following the exit visit, subjects will be advised to see their primary care physician and resume standard treatment to control their diabetes.

If hypoglycemia occurs in any subject prescribed rescue medication for hyperglycemia during the study, the total daily dose of the rescue medication should be reduced 50% or more at the discretion of the investigator.

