If hypoglycemia occurs in any subject prescribed rescue medication for hyperglycemia during the study, the total daily dose of the rescue medication should be reduced 50% or more at the discretion of the investigator.

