3.6. DETERMINATION OF SAMPLE SIZE

Approximately 210 subjects will be randomized 2:1 to bexagliflozin tablets, 20 mg or bexagliflozin tablets, placebo. The sample size calculation for this study was based on a two group t-test with a two-sided significance test at the 5% level and the following assumptions:

- 1. The difference in mean change from baseline to week 24 in HbA1c in the bexagliflozin group compared to that of the placebo group will be -0.5%.
- 2. The standard deviation for the difference in mean change from baseline to week 24 in HbA1c between the bexagliflozin group and the placebo group will be 1.0%.

Under the above assumptions, an estimated sample size of 128 and 64 evaluable subjects in the bexagliflozin and placebo arms, respectively, yielded a 90% power that bexagliflozin treatment will be found to be significantly different from placebo. To account for an estimated drop-out rate of approximately 10%, the study design anticipates randomizing 140 and 70 subjects in the bexagliflozin and placebo arm, respectively.

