Table 14.3.1.1	Overall Summary of Treatment-Emergent Adverse Events (Safety
ומטוכ וא.ט.ו.ו	Analysis Set)

Number	Title
Table 14.3.1.2	Treatment-Emergent Adverse Events by System Organ Class and Preferred Term (Safety Analysis Set)
Table 14.3.1.3	Treatment-Emergent Adverse Events by System Organ Class, Preferred Term and Maximum Severity (Safety Analysis Set)
Table 14.3.1.4	Treatment-Emergent Adverse Events by System Organ Class, Preferred Term and Relationship to Study Drug (Safety Analysis Set)
Table 14.3.1.5	Most Common Treatment-Emergent Adverse Events by System Organ Class and Preferred Term (Safety Analysis Set)
Table 14.3.1.6	Treatment-Emergent Serious Adverse Events by System Organ Class and Preferred Term (Safety Analysis Set)
Table 14.3.1.7	Serious Treatment-Emergent Treatment Related Adverse Events by System Organ Class, Preferred Term and Relationship to Study Drug (Safety Analysis Set)
Table 14.3.1.8	Summary of Treatment Related Treatment-Emergent Adverse Events by System Organ Class and Preferred Term (Safety Analysis Set)
Table 14.3.1.9	Summary of Treatment Emergent Adverse Events Leading to Treatment Discontinuation by System Organ Class and Preferred Term (Safety Analysis Set)
Table 14.3.1.10	Summary of Treatment Emergent Adverse Events of Interest (Safety Analysis Set)
Table 14.3.1.11	Summary of Treatment Emergent Hypoglycemia Events (Safety Analysis Set)
Table 14.3.1.12	Summary of Major Adverse Cardiovascular Events (Safety Analysis Set)
Table 14.3.1.13	Summary of Revascularization and Amputations (Safety Analysis Set)
Table 14.3.2.1	List of Treatment Related TEAEs (Safety Analysis Set)
Table 14.3.2.2	List of Serious Adverse Events (Safety Analysis Set)
Table 14.3.2.3	List of Adverse Events Leading to Treatment Discontinuation (Safety Analysis Set)
Table 14.3.2.4	List of Adverse Events Leading to Death (Safety Analysis Set)
Table 14.3.4.1	Summary of Hematology: Results and Change from Baseline by Visit (Safety Analysis Set)
Table 14.3.4.2	Shift in Clinical Laboratory Values: Hematology (Safety Analysis Set)
Table 14.3.4.3	Summary of Serum Chemistry: Results and Change from Baseline by Visit (Safety Analysis Set)

Version 2.0

THR-1442-C-450

Number	Title
Table 14.3.4.4	Shift in Clinical Laboratory Values: Serum Chemistry (Safety Analysis Set)
Table 14.3.4.5	Summary of Urinalysis: Results and Change from Baseline by Visit - Continuous Variables (Safety Analysis Set)

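### The hypoglycemia summary does not separate events after rescue, so it can understate an excess on bexagliflozin if placebo subjects are rescued more often

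*SAP*

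**What the plan says.** Comparing the incidence of adverse events of special interest with placebo is a safety objective, and hypoglycemia is on the list (Protocol 2.3, SAP 3.3). SAP 9.3.3.2 defines five hypoglycemia categories and then states: "The number and percentage will be summarized by treatment for" each category, and for any severe or documented event. Table 14.3.1.11 is the output, on the Safety Analysis Set.

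Subjects are assigned to an arm by the first kit dispensed (SAP 5.2). Treatment-emergent events are counted from the first double-blind dose, and nothing closes the count at rescue (SAP 9.3).

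Protocol 3.2.3.4 allows rescue with "any approved medication for diabetes that is not otherwise contraindicated, with the exception of an SGLT2 inhibitor", and rescued subjects continue investigational product. Protocol 6.13.11 gives an instruction that begins "If hypoglycemia occurs in any subject prescribed rescue medication for hyperglycemia during the study", so such events are expected. Protocol 3.2.3.3 adds: "After the treatment period, changes to the medical therapy for hyperglycemia should occur at the discretion of the investigator".

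Rescue medication has its own by-arm table and a flag in the medication listing (SAP 7.5.2), but neither is linked to hypoglycemia. For efficacy, two of the three sensitivity analyses in SAP 8.1.2 set post-rescue values aside, by imputation or by carrying forward the value at rescue. No safety analysis does anything similar.

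**The concern.** After rescue, a hypoglycemic event may be due to the added drug rather than to the randomized treatment, yet it counts for the randomized arm. The permitted class is broad enough to include insulin and sulfonylureas.

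The likely direction follows from the design. The trial assumes that the HbA1c change "in the bexagliflozin group compared to that of the placebo group will be -0.5" percentage points, so more hyperglycemia, and hence more rescue, is expected on placebo. Protocol 4.3 admits fasting glucose up to 249 mg/dL at Visit V5. Protocol 3.2.3.4 suggests rescue after week 12 when more than 3 consecutive daily fasting readings are 200 mg/dL or higher. A placebo subject who enters between those levels and does not improve can meet that criterion.

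Extra rescue-drug events on placebo would raise the placebo percentage and make bexagliflozin look better on an event of special interest. From the planned table alone, a reader could not tell whether this had happened.

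**Working it through.** **Plan's own figure.** The documents state no hypoglycemia or rescue rate. The only related figure is the sample size, which supplies the arm sizes. For a "two group t-test with a two-sided significance test at the 5% level", difference 0.5, SD 1.0, 90% power and 2:1 allocation:

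n(placebo) = (1.960 + 1.2816)² × 1.0² × (1 + 1/2) / 0.5² = 63.04, rounded up to 64, with 128 on bexagliflozin.

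This matches SAP 3.6 (power 0.904 by the normal approximation, 0.901 by the t distribution). The planned randomized numbers are 70 and 140.

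**Model A: one risk for all rescued subjects.** Observed risk in an arm = (1 − r) × h0 + r × hr, where r is the share rescued, h0 the risk without rescue and hr the risk in rescued subjects. Assumptions, none from the documents: h0 = 3% placebo and 6% bexagliflozin (true excess 3.0 points); r = 10-20% placebo and 3-5% bexagliflozin; hr = 15-25%.

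In percentage points, the visible difference is 3 + r(bexa) × (hr − 6) − r(placebo) × (hr − 3). Over these ranges it rises with r(bexa) and falls with r(placebo) and hr, so the extremes lie at two corners:

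| Rescue, placebo / bexa | hr | Placebo | Bexa | Difference | Ratio |
|---|---|---|---|---|---|
| 10% / 5% | 15% | 0.90×3 + 0.10×15 = 4.20% | 0.95×6 + 0.05×15 = 6.45% | +2.25 | 1.54 |
| 15% / 5% | 25% | 0.85×3 + 0.15×25 = 6.30% | 0.95×6 + 0.05×25 = 6.95% | +0.65 | 1.10 |
| 20% / 3% | 25% | 0.80×3 + 0.20×25 = 7.40% | 0.97×6 + 0.03×25 = 6.57% | −0.83 | 0.89 |
| 10% / 10% (equal) | 25% | 0.90×3 + 0.10×25 = 5.20% | 0.90×6 + 0.10×25 = 7.90% | +2.70 | 1.52 |

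**Model B: only some rescue drugs cause hypoglycemia.** Observed risk = b + (1 − b) × r × s × h, where b is the risk without rescue (assumed 2% placebo, 5% bexagliflozin; true excess again 3.0 points), s the share of rescue that is hypoglycemia-prone and h the risk on such rescue.

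| Rescue, placebo / bexa | s | h | Visible excess |
|---|---|---|---|
| 10% / 5% | 0.25 | 0.10 | +2.9 |
| 20% / 5% | 0.5 | 0.2 | +1.5 |
| 20% / 5% | 0.5 | 0.3 | +0.8 |
| 30% / 5% | 0.5 | 0.3 | −0.7 |
| 10% / 10% | 0.5 | 0.3 | +2.95 |

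**In subjects.** One placebo subject is 100/70 = 1.43 points and one bexagliflozin subject 100/140 = 0.71 points. In the worst corner of Model A, the placebo percentage rises by 7.40 − 3.00 = 4.40 points, or 0.044 × 70 = about 3 subjects. Power to distinguish 2% from 5% with 70 and 140 subjects is about 15%, so readers will rely on the raw percentages.

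**The case against.** The strongest reply is that an all-events table by assigned arm is a legitimate treatment-policy summary. It matches the primary efficacy analysis, which keeps post-rescue values (SAP 8.1.1). A pre-rescue table stops follow-up at a post-randomization event that probably differs by arm, and removes time from the most hyperglycemic subjects. That stands: such a table should not replace the all-events table.

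Other outputs already help. Hypoglycemia identified by preferred term also falls under SAP 9.3.3.1, which gives rates per 100 patient-years. Adverse events are tabulated by relationship to study drug, rescue is tabulated by arm, and hypoglycemia is listed by subject in Listing 16.2.6.3. With so few events expected, a reader could cross-check by hand. That also stands, but none of these outputs cuts events or exposure at rescue, and a hand check after unblinding is weaker than a pre-specified summary.

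A reader might infer three stronger things that the documents do not support:

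- **Unequal rescue is certain.** It is likely, not certain. Crossing the glucose threshold does not by itself trigger rescue: the criterion needs more than 3 consecutive readings after diet and exercise review, and rescue is then suggested, at the investigator's judgment.
- **Rescue will be insulin or a sulfonylurea.** The protocol names neither as rescue; it only leaves them permitted.
- **The event count is open-ended.** Collection ends at the last scheduled contact, apart from later related serious events (SAP 9.3). Changes of therapy between weeks 24 and 26 are allowed, but subjects are advised to resume treatment after the exit visit, so this is a minor source of noise with no clear direction.

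**Conclusion.** The gap is real and modest. Following the plan mixes rescue-drug events into the only by-category hypoglycemia comparison, most likely in bexagliflozin's favor, and no planned analysis would show by how much.

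The size rests wholly on assumed rates. In Model A a true 3-point excess appears as +2.25 to −0.83 points. Once only part of rescue is hypoglycemia-prone (Model B), the scenarios with up to 20% placebo rescue shrink the excess without reversing it. With equal rescue, +2.70 or +2.95 of the 3.0 points remains visible.

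The comparison is descriptive, so no test or error rate is affected. It would go too far to conclude that the plan does hide an excess, or that the all-events table is wrong. The documents support only that it can understate one and that the reader could not tell.

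**What to change.** Keep the all-events summary. Add to SAP 9.3.3.2 and Table 14.3.1.11 a pre-specified companion with the same categories, restricted to events before the first dose of any rescue or newly started anti-diabetic drug. Report number, percentage and rate per 100 patient-years, with exposure cut at that date. Show the two side by side, neither replacing the other, and flag post-rescue events in Listing 16.2.6.3.

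The cut should use any added anti-diabetic drug rather than the rescue flag, because short courses do not count as rescue. The definitions of rescue also differ: Protocol 5.6 requires at least 2 weeks of continued use, while Protocol 6.14 and SAP 7.5.2 require more than 2 weeks. These passages must be reconciled.

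No new data are needed: medication dates (SAP 7.5) and hypoglycemia dates (Protocol 6.13.11) are already recorded. The cost is a short SAP addition, one more table, and less exposure in the companion, mostly on placebo. Its censoring at rescue is not random, and a footnote should say so.

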9.3.3.3. Major Adverse Cardiovascular Events

Cardiovascular events considered as MACE by investigator will be submitted to an independent CEC for adjudication. The events of interest include cardiovascular mortality, MI, stroke, hospitalization for acute coronary syndromes, urgent revascularization procedures, and other possible serious cardiovascular events. The number, percentage and incidence rate per 100 patient years of suspected MACE and adjudicated MACE will by summarized for each treatment group. Adjudicated MACE will be further summarized by PTs.

9.3.3.4. Revascularization and Amputations

Revascularization and amputations information are collected in a separate form. Frequency and percentage will be summarized for:

- Type of procedures -cardiovascular related or amputation
- Subjects with any amputation
- Conditions that resulted in amputation
- Location of amputation

Only procedures performed after the first dose of double-blind study drug will be summarized.

1007728

9.4. LABORATORY EVALUATIONS

Laboratory tests will include hematology panel, chemistry panel, serum lipids, and urinalysis testing. Hematology, chemistry, serum lipids, and urinalysis will be performed at the following time points: at the screening visit (Week - 11), on baseline visit (Day -3 to -5), and at week 6, 12, 18, 24, and 26. Serum lipids will be performed at the screening visit (Week - 11), on baseline visit (Day -3 to -5), and on week 12, 24, and 26. Renal functional testing by UACR will be determined at the screening visit, on baseline visit and at week 24. The study staff will contact each subject prior to a scheduled clinic visit to confirm the time of the visit and to remind the subject of proper fasting practice. A subject must be queried to assess compliance with an approximately 10-hour fast prior to blood draw to ensure the FPG and triglycerides values can be accurately determined. If a subject has not fasted for approximately 10 hours, the subject must return as soon as can be arranged (within 1 week) to provide a specimen after proper fasting. A list of laboratory tests is included in Table 4.

Low density lipoprotein cholesterol (LDL-C) will be calculated by the Friedewald equation. If triglycerides are > 400 mg/dL, the calculated LDL-C value is invalid by this equation and will be set as missing. Direct LDL-C will be determined in subjects whose triglycerides are > 350 mg/dL at screening visit. All subsequent LDL-C of these subjects will be determined by the same direct LDL-C measurements only. If triglycerides are > 350 mg/dL, a reflex test will be performed based on direct LDL measurement. The following algorithm will be used to obtain LDL-C values for the analyses:

- 1. Select subjects (based on the SI unit) who had screening triglycerides >3.4 or >350 based on the conventional unit
- 2. Take the LDL direct measurement values only, throughout the study visits for those subjects
- 3. If screening triglycerides > 350 and no direct LDL-C values have been determined, take the calculated.

Among those subjects who have screening triglycerides >350 and have both calculated and direct LDL values, only take the direct LDL.

Urinalysis microscopy will be conducted if the subject has a positive result on the leukocyte esterase or nitrite dipstick tests to clarify the significance of the finding. Results of glucose measurement in the urinalysis must be suppressed from the laboratory reports so the sponsor, investigators, study coordinators, pharmacists, study subjects, and the CEC members will remain blinded to the dosing assignment.

The baseline value will be the latest value obtained prior to Day 1. Change from baseline for all continuous parameters will be calculated as the post-baseline value minus the baseline value. All continues variables will be summarized by number of subjects [n], mean, SD, Q1, median, Q3, minimum and maximum and categorical

1007728

variables will be summarized by frequency and percentage.

All scheduled and unscheduled results will be considered in tables that assess maximum grade or toxicity.

Observed values (in SI units) and change from baseline over time will be summarized by treatment group. Laboratory data will be classified as low, normal, or high relative to the parameter's reference range. Laboratory abnormalities for each treatment will also be summarized with shift tables for selected parameters.

All laboratory data will be listed. For hematology, chemistry, and serum lipids, columns will be included for normal ranges and individual abnormal laboratory values will be flagged and clinical significance will be indicated. A listing for the microscopic examination will be provided for subjects who have a positive result from the urinalysis dipstick evaluation.

Table 4 List of Laboratory Tests

Test Name (sample volume)		
Hematology (2 mL blood)		
 Mean corpuscular hemoglobin (MCH) Mean corpuscular hemoglobin concentration (MCHC) 	 Mean corpuscular volume (MCV) White blood cell (WBC) count with differential 	 Red blood cell (RBC) count Hematocrit (Hct) Hemoglobin (Hgb) Platelet count
Serum Chemistry and Electrolyte	es (3 mL serum)	
• Albumin (ALB)	• Calcium (Ca)	• Glucose
• ALT	• Magnesium	• Bicarbonate (HCO ₃)
• AST	• Phosphorus	• Chloride (Cl)
• Blood urea nitrogen (BUN)	• Potassium (K)	 Total bilirubin
• Creatinine	• Sodium (Na)	• Direct bilirubin
• Uric acid	• Total Protein	
Glycemic Control (2 mL plasma,	2 mL blood)	
• FPG	• HbA1c	
Serum Lipids		
 Total cholesterol (TC) High-density lipoprotein cholesterol (HDL-C) 	 Low-density lipoprotein cholesterol (LDL-C), calculated, or LDL-C, direct 	• Triglycerides (TG)
Infectious Disease Testing (3 mL	serum)	
• Hepatitis B surface antigen (HBsAg)	• Hepatitis C virus (HCV)	
Urinalysis		
• Appearance	 Microscopic examination of sediment 	• pH
• Bilirubin	• Nitrite	• Protein
• Color	• Leukocyte esterase	• Specific gravity
• Glucose (blinded)	Occult blood	 Urobilinogen
• Ketones Renal Functional Test		
• UACR		
Urine Pregnancy Test		

1007728

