6.9 Clinical Laboratory Tests

6.9.1 Laboratory Parameters

Clinical laboratory tests are listed in Table 1.

- 6.9.2 Sample Collection, Storage, and Shipping
- 6.9.2.1 Hematology, Blood Chemistry, Serum Lipids, and Glycemic Control Assessments

Blood samples for hematology, chemistry, serum lipids and glycemic control assessments will be collected. Subjects will be in a seated or supine position during blood collection. Samples will be collected at the time points indicated in the schedule of events in Appendix 1 and Appendix 2.

The study staff will contact each subject prior to a scheduled clinic visit to confirm the time of the visit and to remind the subject of proper fasting practice. A subject must be queried to assess compliance with an approximately 10 hours fast prior to blood draw to ensure the FPG and triglycerides values can be accurately determined. If a subject has not fasted for approximately 10 hours, the subject must return as soon as can be arranged (within 1 week) to provide a specimen after proper fasting. Blood samples will be transported to the central lab for analysis. Samples should be stored and shipped as detailed in the Laboratory Manual.

LDL-C will be calculated by the Friedewald equation. If triglycerides are > 400 mg/dL, the calculated LDL-C value is invalid by this equation and will be set as missing. Direct LDL-C will be determined in subjects whose triglycerides are > 350 mg/dL at screening visit. All subsequent LDL-C of these subjects will be determined by the same direct LDL-C measurements only.

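### SAP 9.4 pairs a screening triglyceride cut-off of 3.4 (SI) with 350 (conventional), but 350 mg/dL is about 3.95 mmol/L

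*SAP*

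**What the plan says.** Protocol 6.9.2.1 sets the rule for direct measurement: "Direct LDL-C will be determined in subjects whose triglycerides are > 350 mg/dL at screening visit". Later LDL-C values in those subjects are to come from the direct method only. SAP 9.4 repeats this and adds the validity limit of the Friedewald calculation: "If triglycerides are > 400 mg/dL, the calculated LDL-C value is invalid by this equation and will be set as missing". It also has a sentence on reflex testing: "If triglycerides are > 350 mg/dL, a reflex test will be performed based on direct LDL measurement".

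SAP 9.4 then gives an algorithm for choosing the LDL-C value to analyse:

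- Step 1: "Select subjects (based on the SI unit) who had screening triglycerides >3.4 or >350 based on the conventional unit".
- Step 2 takes only direct values, at all visits, for the subjects selected in step 1.
- Step 3: "If screening triglycerides > 350 and no direct LDL-C values have been determined, take the calculated".
- Closing sentence: "Among those subjects who have screening triglycerides >350 and have both calculated and direct LDL values, only take the direct LDL".

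On reporting, the same section says: "Observed values (in SI units) and change from baseline over time will be summarized by treatment group". SAP 12 declares no departure from the analysis planned in the protocol.

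**The concern.** Step 1 offers the two cut-offs as one limit in two unit systems. If they are not equivalent, the group restricted to direct LDL-C depends on which unit the programmer uses. The lower SI figure would bring in subjects for whom the plan did not order a direct test at screening. The fallback to calculated LDL-C in step 3 is tied to 350, so it would not reach them. Two programmers following the same text could then produce different lipid tables. At stake is the completeness of a descriptive safety summary, not any test or efficacy estimate.

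**Working it through.** **Inputs from the documents**

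- SI cut-off 3.4 and conventional cut-off 350: SAP 9.4, step 1. No unit symbol is printed.
- 350 mg/dL as the trigger for direct LDL-C: Protocol 6.9.2.1 and the SAP 9.4 prose. This identifies the conventional unit as mg/dL.
- 400 mg/dL as the upper limit of validity for calculated LDL-C: Protocol 6.9.2.1 and SAP 9.4.

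**Assumption**

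The documents give no conversion factor for triglycerides. I take a mean molar mass of about 885 g/mol, with a range of 850 to 900 g/mol. The SI unit is read as mmol/L.

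**Formula:** mmol/L = (mg/dL × 10) / molar mass, so the divisor is 88.5 (range 85 to 90).

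**1. Try to reproduce the plan's 3.4 from 350 mg/dL**

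- Triglyceride, central: 350 / 88.5 = 3.95 mmol/L.
- Triglyceride, range: 350 / 90 = 3.89 to 350 / 85 = 4.12 mmol/L.
- Wrong factor for glucose: 350 / 18.016 = 19.4.
- Wrong factor for cholesterol: 350 / 38.67 = 9.05.
- Mass units: 350 mg/dL = 3.50 g/L.

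None gives 3.4. A match would need a molar mass of 3500 / 3.4 = 1029 g/mol. Allowing for rounding of 3.4, the range is 3500 / 3.45 = 1014 to 3500 / 3.35 = 1045 g/mol, well outside the assumed range.

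**2. Convert 3.4 back**

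- Central: 3.4 × 88.5 = 301 mg/dL.
- Range: 3.4 × 85 = 289 to 3.4 × 90 = 306 mg/dL.

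The SI figure thus matches about 300 mg/dL (300 / 88.5 = 3.39). Neither document mentions a 300 mg/dL limit.

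**3. Size of the gap**

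350 − 301 = 49 mg/dL, or 3.95 − 3.4 = 0.55 mmol/L. The SI cut-off is too low by that amount.

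**4. Follow one subject through the algorithm**

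Take screening triglycerides of 3.8 mmol/L, which is 3.8 × 88.5 = 336 mg/dL.

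- Direct-test trigger at screening (350 mg/dL): not met.
- Step 1 coded in SI: 3.8 exceeds 3.4, so the subject is selected.
- Step 2: direct values only, and none was triggered at screening.
- Step 3: 336 mg/dL does not exceed 350, so there is no fallback.
- Calculated LDL-C: valid, because 336 is below 400 mg/dL, but not taken.
- Step 1 coded in mg/dL: not selected, and the calculated value is used as intended.

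The affected band is therefore about 301 to 350 mg/dL at screening. The whole band lies below the validity limit, which is 400 / 88.5 = 4.52 mmol/L.

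**5. Reach in the outputs**

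Protocol Appendix 2 and SAP Table 1 schedule lipids at five visits: screening, baseline and weeks 12, 24 and 26. An affected subject could lose LDL-C at any of these without a direct value. Change from baseline is the post-baseline value minus the baseline value. A subject with no direct value before Day 1 would therefore have no change from baseline at any visit.

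**The case against.** The best defence is that step 1 allows either unit. The SI requirement in SAP 9.4 concerns how observed values are summarised; it does not say that LDL-C selection must run on SI data. If the mg/dL figure is coded, the algorithm matches the prose and nothing is lost. Step 3 and the closing sentence also show the intent, which is to prefer a direct value and otherwise use the calculated one. A sensible programmer might apply that to every selected subject. This stands to the extent that the loss is conditional on a programming choice. It does not remove the contradiction between the two figures. Nor does reading the word or as a union help: the lower SI limit would make 350 redundant and would still conflict with the prose.

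Three stronger readings are tempting, but the documents do not support them.

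- **The unit-free 350 disables the fallback.** A reader might infer that step 3, run on mmol/L data, would never be met, so that subjects truly above 350 mg/dL would also lose their values. Step 1 ties 350 to the conventional unit, and the paragraph above prints it in mg/dL. The missing unit is a matter of clarity only.
- **Missingness depends on treatment.** A reader might infer that a reflex test during the study decides which post-baseline values survive, so that the missing values could differ by arm. The reflex sentence can equally describe how the screening trigger works, and Protocol 6.9.2.1 has no separate on-study reflex test. Selection itself uses screening values, which precede randomization.
- **The shift table is affected too.** Table 14.3.4.9 covers serum lipids, but the text says only: "Laboratory abnormalities for each treatment will also be summarized with shift tables for selected parameters". It does not name LDL-C.

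**Conclusion.** The inconsistency is real and minor. The SI cut-off in SAP 9.4 step 1 is about 0.55 mmol/L (49 mg/dL) below the limit that both documents state in mg/dL. SAP 12 gives no sign of a deliberate change. The conversion factor is an assumption, but the conclusion holds over the whole range of 850 to 900 g/mol.

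The consequence holds only if selection is coded on the SI value. In that case, valid calculated LDL-C is left out of Table 14.3.4.8 for subjects at about 301 to 350 mg/dL at screening, at visits without a direct value. The number of such subjects cannot be derived from the documents. LDL-C is not an efficacy endpoint, the summary is descriptive, and SAP 9.4 still lists all laboratory data.

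**What to change.** Preferably, select on the mg/dL value throughout the algorithm, with the limit written as above 350 mg/dL in step 1, step 3 and the closing sentence. This keeps the sponsor's own limit and needs no outside conversion factor. Alternatively, keep the SI route and replace 3.4 with the SI equivalent of 350 mg/dL, about 3.95 mmol/L, using the central laboratory's factor. In either case, print the unit in step 3 and the closing sentence.

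The cost is a short SAP edit in three places. Data collection does not change and no protocol amendment is needed.
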